	
 
Caregiver Administered Children's Acceptance Tool (CareCAT).
 
 
Safety Assessments:
 
 
Physical examination and vital signs;
 
Growth assessments (length, BW, head circumference);
 
Hypo- and hyper- thyroidism signs and symptoms; and
 
Adverse events (AEs).
 
 
Other Assessments:
 
 
Dosing evaluation;
 
Treatment compliance; and
 
Nutritional intake.
 

Main Outcomes:	
 
Daily LT4 dose/kg required to maintain TSH in target range;
 
Frequency of dose adjustments;
 
Overall TSH, FT4 and, where available, TT4 values;
 
The number of events (TSH values) above 4.5 mU/L for TSH;
 
The number of events (FT4 values) below the middle of the laboratory normal range for FT4 for age;
 
Presence of signs and symptoms of hypo- and hyper-thyroidism;
 
Acceptance of medications evaluated by means of the CareCAT;
 
Ease of administration evaluated by means of Parents' Satisfaction Questionnaire; and
 
Growth patterns: 
 
Length;
 
BW;
 
Head circumference.
 
 
 

Exploratory Outcomes:	
For newly diagnosed neonates:
 
 
Time to normalize TSH into reference range; and
 
Time to normalize FT4 into the upper half of the laboratory normal FT4 range for age.
 

Statistical Methods:	
Sample size:
 
Subjects will be randomized in a 2:1 ratio to Treatment (Tirosint®-SOL) or Control (conventional therapy with levothyroxine sodium crushed tablets). Considering a mean value of 6 mcg/kg/day of LT4 dose at 12 months of age and a standard deviation of 2 mcg/kg, a sample size of 102 neonates and infants (68 Treatment and 34 Control)

will have 80% power to detect a difference of 20% in the LT4 dose between the groups using an independent t-test with a 0.050 two-tailed significance level. To account for a drop-out rate of maximum 20%, 126 neonates and infants will be enrolled in the study (84 Treatment and 42 Control).

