Von Heppe reported that in 28 newborns with primary CH, the initial dose necessary to normalize TSH is not lower when a liquid solution is used. The higher dose used in tablets is not due to inefficient absorption, but rather reflects the increased demand for TH in the first weeks of life. The liquid formula was easier to handle for the parents, and enabled more individualized dosage of newborns, especially those with a LBW. In comparison with parents whose children received LT4 in tablet form, the parents of newborns who received the liquid formula were more content with the treatment ([von Heppe 2004](#)).

Further knowledge on the use of LT4 oral solutions in the pediatric population has been gained recently.

A multicenter study compared the effectiveness of an LT4 oral solution (group D, 117 subjects) with that of a tablet formulation (group T, 137 subjects) in children with CH up to 3 years of age. Auxological parameters, LT4 dose and thyroid function values (TSH and FT4) at diagnosis, 3, 6, 12, 24, 36 months were not significantly different. TSH at 15 days ( $p = 0.002$ ) and 1 month ( $p = 0.009$ ) was significantly reduced in group D. At 2-year follow-up, median TSH was significantly lower in group T ( $p = 0.03$ ). Both therapeutic strategies were considered effective in the treatment of CH, with a higher risk of overtreatment in the first months of therapy associated with oral solution. No negative effects on cognitive development were observed ([Vigone 2021](#)).

A prospective randomized control study compared a liquid LT4 formulation available in Greece (Group B, 19 subjects) with tablets (Group A, 17 subjects) in the substitutive treatment of 3-12 years old children with CH, who were evaluated at 0, 2, 4 and 6 months. TSH values showed a statistically significant difference ( $p=0.017$ ) between groups only at 6 months (Group A having higher TSH levels than Group B), while FT4 levels had no statistical difference throughout the 6-month study period and were always within the normal range. Dose adjustments were more frequent in Group A ( $p=0.038$ ). Liquid LT4 substitutive treatment exhibited no statistically significant adverse effects in comparison to tablets ([Tzifi 2021](#)).

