## 9 RISK-BENEFIT ASSESSMENT

### 9.1 KNOWN POTENTIAL RISKS

It is known that LT4 is well tolerated for the treatment of CH. Potential risks related to its use in the pediatric population are as follows:

- Infants with CH appear to be at increased risk of other congenital anomalies. Cardiovascular anomalies, including pulmonary stenosis, atrial septal defect, and ventricular septal defect are the most common (AAP 2006).

- Subjects should be closely monitored during the first two weeks of LT4 therapy for cardiac overload, arrhythmias, and aspiration from suckling ([Synthroid USPI](#), [Tirosint®-SOL USPI](#)).
- Undertreatment may have deleterious effects on intellectual development and linear growth ([Synthroid USPI](#), [Tirosint®-SOL USPI](#)).
- Overtreatment has been associated with craniosynostosis in infants, and may adversely affect the tempo of brain maturation and accelerate bone age with resultant premature closure of the epiphyses and compromised adult stature ([Synthroid USPI](#), [Tirosint®-SOL USPI](#)).
- Potential risks due to switching from tablets to liquid solution in infants, are considered minimal in the conduct of this study due to titration method implemented while switching and will be further mitigated by the frequency of study visits. Switching from tablets to liquid solution does not apply to neonates.

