### **19.3.4 SAFETY OUTCOMES**

Vital signs at each in-person visit will be analyzed descriptively within treatment groups.

Length, weight and head circumference will be analysed at each in-person visit by means of basal value, treatment group, newly diagnosed neonates vs infants already on LT4 therapy, age at inclusion and center as covariate.

The presence of signs and symptoms of hypo- and hyper-thyroidism at each planned visit will be compared between treatment groups by means of Chi test.

Number of subjects experiencing AEs and SAEs during the study will be calculated. Number of AEs and SAEs will also be calculated. Difference between treatment groups on subjects who experienced AEs and SAEs will be evaluated using a Chi test or a two-tailed Fisher's exact test as appropriate. Moreover adverse events will be described by MedDRA's System Organ Classes (SOCs) and Preferred Term (PT).

Similar summary tables will be provided for the number of AEs/SAEs at least possibly related to study treatment and for the number of AEs/SAEs leading to study discontinuation.

The number and percentage of subjects with AEs/SAEs will be summarized by their MedDRA preferred term within SOC.

Any subject reporting multiple episodes of the same AE/SAE (i.e. same preferred term) will be counted once.

Compliance will be calculated as the percentage of medication taken in relation to the recommended dose and the actual period of treatment (number of doses reported to be taken / number of doses envisaged x 100). Treatment Compliance will be described by means of descriptive statistics.

The number of subjects who need a dose re-adjustment during the long-term follow-up phase of the study will be compared between treatment groups by means of Chi test.

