7 SAFETY AND TOLERABILITY VARIABLES

Signs and symptoms of hypo-/hyper-thyroidism

Total number of subjects experiencing hypothyroidism/hyperthyroidism signs and symptoms.

Physical examination

The following information about abnormalities found during the examination: body system, findings and clinical significance.

Vital signs

Vital signs that will be collected and recorded in the EDC are heart rate and temperature.

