The mixed model will be adjusted with Kenward-Roger method and the unconstructed covariance matrix will be used as first choice (other matrixs will be considered if there will be convergence problems).

Summary descriptive statistics will be provided for Parents’ Satisfaction Questionnaire score and the results at each visit will also be compared between treatment groups by Wilcoxon Mann-Whitney test.

Caregiver Administered Children’s Acceptance Tool (CareCAT)

The subject medicine acceptance assessed by “Caregiver Administered Children’s Acceptance Tool (CareCAT)” will be analyzed during the first week, the third week, and the eighth week

of administration and analyzed by day in each week and by week comparing the treatment groups by means Cochran-Mantel-Haenszel χ^2 test. Descriptive statistics on aggregate CareCAT results overall and by week will also be provided.

Dose re-adjustment

The number of subjects who need a dose re-adjustment during the long-term follow-up phase (Visit 4 to Visit 11) of the study will be compared between treatment groups by means of Chi-squared test or, when the expected values in any of the cells of a contingency table are below 5 or the total number of observations is less than 20, Fisher exact test as appropriate.

Growth pattern

Summary descriptive statistics on length (cm), weight (Kg) and head circumference (cm) will be provided. Results at each visit for each parameter will be compared between treatment groups by Wilcoxon Mann-Whitney test.

Growth assessment parameters will also be listed with clinically significant information.

Signs and symptoms of hypo- and hyper-thyroidism

Number of subjects experiencing hypothyroidism/hyperthyroidism signs or symptoms will be summarized by hypothyroidism, hyperthyroidism and overall.

The number of subjects experiencing at least one sign or symptom will be compared between treatment groups using a Chi-squared test or, when the expected values in any of the cells of a contingency table are below 5 or the total number of observations is less than 20, Fisher exact test as appropriate.

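### The one planned between-arm test of thyroid signs, as worded, counts hypothyroid and hyperthyroid signs together and so cannot separate under-treatment from over-treatment

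*SAP*

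**What the plan says.** The Main Outcomes in the protocol synopsis include "Presence of signs and symptoms of hypo- and hyper-thyroidism". Protocol 19.3.4 plans the comparison by visit: "The presence of signs and symptoms of hypo- and hyper-thyroidism at each planned visit will be compared between treatment groups". It does not say whether hypothyroid and hyperthyroid signs are taken together or apart.

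SAP section 7 defines the variable as one total: "Total number of subjects experiencing hypothyroidism/hyperthyroidism signs and symptoms". SAP 9.4.2 then has two consecutive sentences. In the first, subjects with signs or symptoms are "summarized by hypothyroidism, hyperthyroidism and overall". The second gives the test: "The number of subjects experiencing at least one sign or symptom will be compared between treatment groups", by chi-squared or Fisher's exact test. The test sentence names no direction and no row of the summary.

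Two other parts of the plan bear on this:

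- The two binary laboratory events in SAP 6.1.2 are TSH above 4.5 mU/L and FT4 below the middle of the laboratory range.
- Protocol 8.1 summarises a prospective study of 42 newborns with significantly more suppressed TSH on liquid than on tablets, and a multicenter study with a "higher risk of overtreatment in the first months of therapy associated with oral solution".

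**The concern.** Hypothyroid and hyperthyroid signs are opposite failures of the same treatment: too little hormone and too much. Protocol 9.1 lists under-treatment and overtreatment as separate risks with different consequences. A count of children with any sign adds the two, so an arm with fewer hypothyroid signs and more hyperthyroid signs can show the same total as the other arm.

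A non-significant result could then be reported as no difference in clinical signs when the mix differs. A significant result would not say which failure differs.

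The rest of the plan only partly fills the gap. Both binary laboratory events look at under-treatment, and no event for low TSH or high FT4 is planned. The dose re-adjustment count has no direction. SAP 10.1.1 summarises adverse events without a between-arm test. No planned categorical comparison is therefore directed at over-treatment.

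**Working it through.** **Plan's own figure.** The documents give no sign rate, effect size or power for this test. The only sample-size calculation concerns LT4 dose/kg. It reproduces: 1.5 × (1.96 + 0.84)² × (2/1.2)² ≈ 33 controls, so 33 + 66 = 99 against the stated 102, and power at 68 vs 34 is about 81%. It has no bearing on the signs test.

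**Inputs.**
- Number randomised: 31 (SAP section 3), at 2:1 (SAP 3.3). The split by arm is not given. Since 31 × 2/3 = 20.7, I assume 21 on solution and 10 on tablets.
- Significance: p rounded to three decimals and below 0.050 (SAP 9.1).
- Test: chi-squared, or Fisher if any expected cell is below 5 or there are fewer than 20 observations (SAP 9.4.2). At 21:10 this is always Fisher, because the smallest expected cell is at most 10 × 15/31 = 4.8.
- All sign rates below are assumptions.

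**One possible table at 21:10, with the two kinds of sign in different children.**

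| Subjects with | Solution | Tablets | Risk difference | Fisher p |
|---|---|---|---|---|
| Hypothyroid sign | 2/21 (9.5%) | 6/10 (60%) | −50.5 points | 0.006 |
| Hyperthyroid sign | 12/21 (57.1%) | 1/10 (10%) | +47.1 points | 0.020 |
| Any sign | 14/21 (66.7%) | 7/10 (70%) | −3.3 points | 1.00 |

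When no child has both kinds, the difference for any sign is the sum of the other two, apart from rounding. That is the offset. It is complete only when the two shifts are equal and opposite.

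**Chance of significance.** Power is the sum of Bin(a; 21, p_solution) × Bin(b; 10, p_tablets) over all tables (a, b) that the rule calls significant. With the two kinds independent within a child, the rate for any sign is 1 − (1 − p_hypo)(1 − p_hyper). Row 1, for example, gives 1 − 0.60 × 0.95 = 43% on tablets and 1 − 0.90 × 0.60 = 46% on solution. Row 3 instead puts the two kinds in different children, so the rates add.

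| Row | Tablets hypo/hyper | Solution hypo/hyper | Any sign, tablets vs solution | Combined test | Hypo test | Hyper test |
|---|---|---|---|---|---|---|
| 1 | 40%/5% | 10%/40% | 43% vs 46% | 3% | 41% | 45% |
| 2 | 30%/10% | 10%/30% | 37% vs 37% | 3% | 21% | 11% |
| 3 | 40%/10% | 20%/40% | 50% vs 60% | 5% | 16% | 30% |
| 4 | 20%/5% | 10%/10% | 24% vs 19% | 4% | 8% | 0.2% |

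A 20:11 split changes little: row 2 becomes 3%, 24% and 14%.

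**Is this only a small-sample problem?** At the planned 84 vs 42, the SAP's own chi-squared/Fisher rule gives 5%, 79% and 76% for row 2, and 19%, 66% and 97% for row 3. The combined test stays at its false-positive level when the shifts are equal and is weakened when they are not. What is counted causes this, not the number of children. These figures only illustrate the mechanism, since enrolment closed at 31.

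**Cost in error rate.** Two independent tests at 0.05 carry a chance of 1 − 0.95² = 9.75% of at least one false positive.

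**The case against.** The strongest reply is that the split is already planned. The sentence before the test requires signs to be shown by direction, so a trade of one failure for the other would appear in the same table. That stands. A reader might infer that the analysis would hide such a shift altogether, but the documents do not support this. TSH and FT4 are also compared between arms at each visit, by mixed model and Wilcoxon test (SAP 9.4.2), and those comparisons carry direction.

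The test sentence could also be meant for each of the three rows. The SAP does not say so, and its section 7 defines a single total. If that was the intention, one clarifying sentence settles the matter.

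A reader might further infer that oral solution is known to produce more hyperthyroid signs, or that the protocol ties craniosynostosis to it. Neither is documented:

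- The evidence in Protocol 8.1 is mainly biochemical and concerns LT4 oral solutions in general. No cited study is described as finding a difference in hypothyroid or hyperthyroid signs. The 42-newborn study found no clinical or electrocardiographic signs of heart disease. The multicenter study found lower median TSH on tablets at two years.
- The statement in Protocol 9.1, "Overtreatment has been associated with craniosynostosis in infants", is a general LT4 risk taken from both the tablet and the solution labels.
- The overtreatment risk was reported for the first months of therapy. Only 4 of the 31 children were newly diagnosed neonates (SAP 3.4); the other 27 entered already on LT4, and doses are adjusted to laboratory values in both arms.

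Finally, SAP 9.4 calls all efficacy analyses exploratory, and no decision depends on this test. That limits how serious the point is. It does not make the combined count informative.

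**Conclusion.** The point holds in a limited form. On its plain wording, the only between-arm test of thyroid signs cannot tell under-treatment from over-treatment: opposite shifts are diluted, and cancel when they are about equal. The descriptive rows and the continuous TSH and FT4 comparisons remain as safeguards. The gap still matters because neither binary laboratory event looks at over-treatment and the protocol's own background raises that concern for LT4 oral solutions.

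The size rests on assumed sign rates, an assumed 21:10 split and, except where stated, independence of the two kinds of sign within a child. Where the shifts nearly offset, the combined test is significant about 3% to 4% of the time. It would be wrong to infer that separate tests would reliably find a shift at N = 31. Their power runs from about 8% and 0.2% under the mild rates to 41% and 45% under the strong ones, and under the mild rates the hyperthyroid test does worse than the combined one. The main gain is an estimate and interval for each direction, not the p-values. This is a worthwhile correction to an exploratory analysis and does not threaten the trial's conclusions.

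**What to change.** In SAP 9.4.2, replace the single test sentence with two comparisons under the existing chi-squared/Fisher rule: subjects with at least one hypothyroid sign or symptom, and subjects with at least one hyperthyroid sign or symptom. Give each a risk difference with a 95% CI, and name the interval method in advance because cells will be small. Keep the overall row as description, without a test. Align the single total in SAP section 7 with this.

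No new data are needed, since the summary in SAP 9.4.2 already requires the hypothyroid/hyperthyroid category. The cost is a sentence or two of text and one extra unadjusted exploratory p-value, to be labelled as such. If the analysis has already been run under SAP version 2.0, report the split as an addition and explain it in the statistical report, as SAP section 1 provides for deviations.

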10 ANALYSIS OF SAFETY

Safety analysis will be performed on Safety Analysis Set (SAF).

10.1 Tolerability parameters

10.1.1 Adverse Events

The total number and percentage of subjects with at least one Adverse Event (AE), treatment-emergent Adverse Event, serious Adverse Event, drug-related Adverse Event, Adverse Event leading to treatment discontinuation and Adverse Event leading to death will be summarized by treatment group.

The following summary tables by treatment group will also be provided:

- Adverse Events by System Organ Class (SOC) and Preferred Term (PT);
- Serious Adverse Events by System Organ Class (SOC) and Preferred Term (PT);
- Treatment-Emergent Adverse Events by System Organ Class (SOC) and Preferred Term (PT);
- Drug related Treatment-Emergent Adverse Events by System Organ Class (SOC) and Preferred Term (PT);

10.1.2 Vital signs

Summary descriptive statistics on heart rate and temperature will be provided by treatment group.

Vital signs will also be listed with clinically significant information.

10.1.3 Physical examination

Summary descriptive statistics on body systems and findings of abnormal physical examinations will be provided.

Abnormal physical examination information will also be listed with the following information: body system, abnormal finding and clinically significant.

10.1.4 Other tolerability parameters

Compliance

Compliance will be computed for each subject by visit considering as start date the first date of treatment after randomization reported on the LT4 treatment forms and as end date the Date of Last Study Drug Dose Taken reported in the end of study form.

The number of expected days of treatment will be computed by visit for each subject and the number of days of treatment will be computed based on the study medication diary considering the autofilled treatment day number with information about time of administration or strength not missing.

Due to the lack of adherence with the compilation of the daily diary, compliance will be calculated and reported for informative purposes only.

10.2 INTERIM ANALYSIS

No interim analysis is planned for this study.

10.3 SOFTWARE TO BE USED

All statistical analyses and data processing will be performed using SAS® Version 9.4 on a Windows operating system.

10.4 CODING DICTIONARIES

Adverse Events, medical history and previous and concomitant medications will be coded using the following dictionaries: MedDRA (version 24.0) and WHO Drug Dictionary (version March 1, 2021).

12 APPENDIX 1: LIST OF TABLES, LISTINGS AND FIGURES

Not applicable.

13 APPENDIX 2: SHELL TABLES, LISTINGS AND FIGURES

Not applicable.

14 APPENDIX 3: PARENTS' SATISFACTION QUESTIONNAIRE SCORES.
